2.5 Safety/Risk Profile

The risk assessment for the application of ALX-0081 can currently be determined on the basis of the preclinical data available, the data from the 3 Phase I studies in healthy volunteers and in patients with stable angina undergoing a PCI procedure, the postulated mode of action, the clinical presentation of patients with vWD and the knowledge of other generally used antithrombotic agents. In this respect, it is noteworthy that so far, preclinical models have been highly predictive for the human situation in terms of PK/PD and safety.

2.5.1 Potential Risks

Toxicity

Subchronic toxicity studies of ALX-0081 (13 weeks) have been performed in cynomolgus monkeys and guinea pigs. In both studies the NOAEL proved to be above 4x10 mg ALX-0081/kg body weight, the maximum allowable volume of administrations per day for a guinea pig or cynomolgus monkey study. The biomarker RICO was inhibited during the toxicity studies, thereby indicating the absence of neutralising antibodies against ALX-0081. Comparing the results obtained with the 13 weeks cynomolgus monkey toxicity study with a fixed daily dose of 10 mg in humans, revealed a Ratio_{AUC24} of 82, demonstrating the presence of wide therapeutic window. Using PK modeling a predicted human exposure of 10.3 µg.h/mL (AUC_{24h}) following a possible bid 10 mg administration (20 mg/subject/day) can be compared to exposure reached in toxicity studies with a resulting ratio of 54 for cynomolgus monkey. Due to the conservative correction factor applied in the exposure margin calculations of guinea pigs and the limitations in volume that could be administered to guinea pigs, a 10-fold systemic exposure margin could not be demonstrated in the guinea

pigs. Importantly, the NOAEL was not reached during the subchronic toxicity study in guinea pigs.

Hence the data obtained from the 13 weeks cynomolgus monkey study allow us to conclude that the safety margins in terms of relative systemic exposure to ALX-0081 can be considered as very wide.

Risk for bleeding

The most prominent risk of the currently used non-specific antithrombotic agents is an elevated bleeding diathesis or apparent bleeding. Beside any unexpected effects, bleeding also represents the most relevant safety concern for ALX-0081. In this context ALX-0081 was investigated in a preclinical surgical bleeding model.¹¹ In this study, surgical blood loss in animals receiving ALX-0081 was comparable to blood loss in Heparin[®] treated animals, and 2- and 4-fold less than in Plavix[®] and ReoPro[®] treated animals, respectively. This indicates that ALX-0081 may be safer than Plavix[®] and ReoPro[®] in terms of bleeding risk. The ALX-0081 doses used in this surgical bleeding model were more than 10-fold the documented effective antithrombotic dose.

In the 13-week and 26-week RD toxicity studies in cynomolgus monkey, anti-FVIII antibodies (AFA) were detected in 4 male animals with no associated clinical signs, and in one animal with associated haemolytic anaemia, signs of inflammation and extremely low FVIII:C activity. More details are included in Section 4.3 of the Investigator's Brochure.

A good understanding of the biology of vWF and the clinical presentation of patients with deficiency of vWF helps to understand the observations seen in the conducted preclinical and clinical studies and to assess the risk for bleeding appropriately. It is well known that most patients suffering from a deficiency of vWF (vWD) have mild-to-moderate quantitative deficiencies of vWF and FVIII, which are co-ordinately reduced to 5 to 30 percent of normal plasma levels (5 to 30 IU/dL).¹² This reduction is not associated with spontaneous bleeding but with bleeding after surgery (which is typical of coagulopathies) and mucosal tract haemorrhages such as epistaxis and menorrhagia (which are typical of thrombocytopathies). It should be taken into account that these patients have a chronic, i.e. life-long, impairment of vWF and their vWF levels always stay far below 30 IU/dL. These patients don't receive regular prophylaxis, because their bleeding tendency is less severe. Only in patients with chronic and complete absence of vWF or levels below 5-10 IU/dL is a prophylaxis with vWF and FVIII indicated.

Since ALX-0081 interacts with the A1 domain of vWF, RICO is inhibited also during the toxicity studies. In addition, statistical significant drops in FVIII and vWF:Ag levels were observed in cynomolgus monkeys. In guinea pigs, the observed effects on FVIII were less pronounced. Although drops for FVIII were observed in both species, sufficient FVIII remained available to ensure proper coagulation (see also 2.3.3). No signs of bleeding, other than bruising at the injection sites were observed in the guinea pig study. In the cynomolgus monkeys study, slightly increased bleeding at injection sites were recorded in one male (4 mg/kg/day) and two females (4 and 40 mg/kg/day). Mucosal bleedings (1 exaggerated menstrual bleeding and 1 nose bleed) were observed in the same females. Importantly, although systemic exposure reached levels up to 80-fold higher than what can be expected in men during the Phase II trial, no signs of internal bleeding were observed. The observed clinical effects in cynomolgus monkeys are in line with the clinical presentation of patients with a mild to moderate vWD.

From the safety data collected from the Phase I studies in healthy volunteers and patients with stable angina, a single i.v. administration of 0.5 mg up to 12 mg and respective multiple administrations up to 18 mg total dose of ALX-0081 as a short infusion over 1 hour were well tolerated in all participating subjects. The observed mild decreases in FVIII and vWF levels were expected as they indicate the biological effectiveness of the drug. None of the observed decreases in FVIII chromogene or vWF levels were recorded as clinically significantly.

In healthy subjects, s.c. administration of ALX-0081 as a SD or administered as daily injection for up to 14 days was well tolerated and no difference could be detected regarding the number of subjects with AEs and their severity. All injection and puncture site reactions were of mild intensity and were classified as clinically not relevant. S.c. administration of ALX-0081 as a SD or administered as daily injection for up to 14 days resulted in a fast and reversible decrease of FVIII and vWF. The average decrease of vWF levels ranged from approximately 50% decrease in low dose groups to 70% decrease, compared to pre-dose level, in the high dose groups. For FVIII, a rapid average decrease can be found in all doses groups ranging from 30%, compared to pre-dose level, in the 2 mg dosing group to 50-65% in the other SD groups. Reversal takes place after approximately 72 h after dosing. A sustained decrease of approximately 50% can be found after dosing in both MD groups. Levels are back to basal levels after approximately 48 h post dosing in the MD groups. None of the observed decreases in FVIII were recorded as abnormal/clinically significant PD assessments or as AEs.

In summary, in all healthy subjects and patients with stable angina, the treatment with ALX-0081 resulted in a rapid and reversible reduction of vWF and FVIII levels, but this reduction never reached the levels indicating spontaneous bleeding for patients with mild or

more severe forms of vWD. It is therefore expected that the further administration of ALX-0081 does not result in a clinically significant reduction of vWF and FVIII mandating prophylaxis or treatment for an imminent bleeding risk. Of note, vWF as antidote is readily available in the respective treatment institutions and would immediately antagonise the activity of ALX-0081 and Preclinical studies have demonstrated that vWF concentrates can indeed antagonise the activity of ALX-0081.

Immunogenicity

ALX-0081 is structurally not identical to an endogenous protein and has no agonistic function. Consequently, the risk for developing antibodies with potential adverse consequences such as the neutralisation of an endogenous protein or a hyper-agonistic function is considered to be low. At present, the development of ADA after i.v. and after s.c. administration of ALX-0081 has been evaluated in the conducted Phase I trials. I.v. treatment during the Phase I trials consisted of either SD treatment or MD administrations with 4 doses during 24 h. S.c. treatment included repeated daily administration of ALX-0081 for up to 14 days. In none of the Phase I trials, treatment-emergent ADA were observed. During the planned Phase II TTP trial, ALX-0081 will be given on top of current standard of care treatment, thereby limiting the potential consequences of the development of ADA. For many of these TTP patients, immunosuppressive treatment will be part of their standard of care treatment. Other TTP patients carry an underlying disease (e.g. human immunodeficiency virus (HIV) or cancer) associated with a depressed immune status. In both groups of TTP patients the probability for development of ADA is anticipated to be reduced.

2.5.2 Potential Benefits

Although the introduction of PE and transfusion has significantly reduced the mortality rates from TTP over the last three decades, the condition still carries a significant risk of mortality and morbidity. The mortality rate of acute bouts in acute idiopathic TTP, in patients managed with the current therapies remains in the order of 10% to 30%.^{1,13,14} In the case of secondary TTP, PE and transfusion are recognised to be less effective and the mortality rate is considerably higher. In the cases when the disease is secondary to pregnancy, in which PE is regarded as reasonably effective the mortality rate of an acute bout of TTP is approximately 25%, rising to over 40% in cases with concurrent pre-eclampsia.¹⁵ However, in cases secondary to, for example, underlying malignancies or bone marrow transplant the mortality rate remains at 40% to 60% despite the use of such treatment regimens.^{14,16,17}

Potential effect of ALX-0081 on pathophysiology of TTP

ULvWF-mediated platelet aggregation is recognised as a key element in the pathogenesis of idiopathic TTP both in acute disease, in refractory and relapsing patients, and in the familial form of the disease. In secondary TTP, although the underlying etiologies are varied, ULvWF also appears to play a fundamental role in the underlying pathophysiological processes that have been proposed to underlie the condition. The inhibition of ULvWF-mediated platelet aggregation represents a rational approach to treatment that may prove to be of value in the management of all subtypes of TTP. Given the continuing significant level of mortality from TTP and the observed complications of PE and transfusion, there is a clear need for the development of such additional therapeutic approaches to supplement, or potentially reduce the need for, these methods of treatment. On the basis of the available information, ALX-0081 may offer such an additional option to further improve the management of TTP.

Potential benefit of ALX-0081 in TTP: efficacy

For acquired TTP, the hypothesis of the proposed Phase II trial is to demonstrate a decrease of 44% in the time-to-response, objectivated by a recovery of platelets $\geq 150,000/\mu\text{L}$. Platelet count increase is a sign of diminished pathological platelet aggregation, as well as a better protection against bleeding. The decrease of LDH is a sign of decreased haemolysis and/or tissue ischaemia. This response must be confirmed up to 48 hours after the time-to-response.

Potential benefit of ALX-0081 in TTP: safety

While a more rapid recovery from TTP and a potential for a reduction in exacerbations and relapses would be of clear clinical benefit in terms of treatment efficacy, the potential for a reduction in the duration and frequency of PE and transfusion would also provide additional benefits in terms of patient safety.

Although PE and transfusion are currently regarded as the standard treatment in the management of TTP, the procedures carry the risk of significant complications. The PE procedure requires high fluid volumes and flow rates necessitating the use of central venous dual lumen haemodialysis catheters. Complications from the procedure include haemorrhage from catheter insertion, sepsis, catheter thrombosis, pneumothorax, fluid overload, hypoxia and hypotension.¹⁸⁻²² Anaphylactoid reactions complicate 0.25% to 0.5% of procedures.^{13,19} In addition, the infusion of plasma containing blood products can cause a non-infective TRALI. This condition is recognised as one of the most frequent causes of transfusion-related fatalities with an incidence estimated to be 0.02% to 0.05% per plasma containing unit¹⁸ with a daily average of 17 plasma units, the daily risk can be calculated to a range of 0.34% to 0.85%. Most patients with TTP require multiple PEs and transfusions. Patients with acute idiopathic TTP require daily treatments, and an average of approximately 16 treatments is required to achieve remission.¹³ In refractory cases the frequency of treatment may be increased to twice-daily.¹³ In the case of patients with familial TTP, regular prophylactic plasma infusions at two to three week intervals are recommended.²³ Anaphylaxis and TRALI thus represent clear risks to patients with TTP whose treatment requires such a frequency and regularity of PEs and transfusions. While it is thought that this risk may be lower if solvent/detergent (S/D) treated plasma is used instead of fresh frozen plasma, the use of large volumes of S/D plasma may be associated with an increased risk of venous thromboembolism.^{13,18} Overall, it is estimated that approximately 30% to 40%

of patients will experience adverse effects from PE and transfusion, and the mortality rate from the procedure is of the order of 2% to 3%.^{2,19}

As summarised above, the information currently available from the preclinical and clinical studies with ALX-0081 also indicates that it is a well tolerated agent and, in particular, the potential for the risk of bleeding appears to be low. The currently available data suggest, therefore, that the potential reduction in PE and transfusion and their associated complications may be achieved without significant adverse effects from the use of ALX-0081 itself. If this is borne out in clinical research, it could represent a clear safety benefit for the use of the product in the treatment of patients with TTP.

Potential benefit of ALX-0081 in TTP: quality of life

Following recovery from a bout of TTP, many patients describe cognitive abnormalities for many years and report troublesome problems with memory, concentration, decreased energy and fatigue. Such symptoms have a negative impact on the quality of patients' daily lives. Furthermore, this deficit in quality of life may occur in all patients who have TTP, regardless of the aetiology and severity.²⁴ It is thought that these symptoms may be reflective of the residual effects of tissue ischaemia. On this basis, it could be reasonably proposed that the potential for a more rapid recovery from TTP and the limitation of thrombus formation in the microvasculature that ALX-0081 should provide, may result in an improved longer-term outcome for the patients in terms of their quality of life.

Summary

The research conducted into TTP over the past three decades has improved the understanding of the pathophysiology of the disease allowing for the potential development of novel agents targeting the underlying disease processes. There are no currently approved therapies for TTP, and although there are newer therapies currently undergoing evaluation, the studies of these potential treatments are at a relatively early stage.

ALX-0081 represents a novel approach to the treatment of TTP and the information available from *in vitro*, *in vivo* and early clinical studies all suggest a clear rationale for its use in this disease and a reasonable expectation that it will provide significant benefit in terms of efficacy, safety and quality of life for patients with TTP.

Through its inhibition of ULvWF-mediated platelet aggregation and resulting antithrombotic effect ALX-0081 may permit more rapid control of acute bouts of TTP when used in combination with PE and transfusion. This would potentially reduce the risk of organ ischaemia and a more rapid normalisation of the platelet count could also reduce the risk of haemorrhagic complications. Its use may also result in improved outcomes in poorly responsive patients, including those with secondary TTP where mortality from the disease

remains high. In addition, ALX-0081 may be of value in the prevention of relapses after recovery from an acute episode.

2.6 Rationale for Dose Selection

The initial i.v. administration of investigational drug prior to the first PE on study is justified based upon a Phase I study in healthy volunteers as well as a Phase Ib trial in ACS patients. In both studies, an immediate PD effect was observed, namely RIPA \leq 10% in healthy volunteers and RICO \leq 20% in ACS patients (see section 2.4). It is believed that all active ULvWF present in the blood that has not yet aggregated platelets can be inhibited from further platelet aggregation by saturating it with the immediate i.v. injection of 10 mg anti-vWF Nanobody. This would allow for predicted protection by the investigational product against further platelet aggregation until the time of start of PE therapy.

The further administrations of the investigational drug will be performed by the s.c. injection route. The proposed s.c. dosing regimen of the ALX-0081 was investigated in a Phase I study with healthy volunteers. The daily dosing of ALX-0081 10 mg as s.c. injection resulted in a complete and sustainable inhibition of the biomarker RICO indicating the complete suppression of vWF-mediated platelet aggregation. PK modeling of these subjects with normal vWF pre-treatment levels demonstrated that the required occupancy of the target vWF resulting in maximum PD effect (i.e. RICO \leq 20%) is seen for a wide range of ALX-0081 plasma concentrations, i.e. between 100-500 ng/mL for 7 treatment days and between 100-350 ng/mL for 14 treatment days. This implies that the maximum pharmacological effect can already be achieved at relative low plasma levels of ALX-0081. Taking into consideration that vWF plasma concentrations in patients with signs and symptoms of TTP can be considerably higher than in healthy volunteers, these data suggest that the proposed doses allow for full target occupancy and subsequent complete inhibition of the biomarker in patients with vWF levels within the range of 1 to 3 fold above the previously studied levels in healthy subjects and patients suffering from ACS. This range of target occupancy (i.e. saturation of plasma vWF) lies within the reported levels of plasma vWF for patients undergoing PE as treatment for TTP.^{25,26}

The dosing scheme allows for a study drug treatment interruption based on clinically significant adverse drug reaction (i.e. bleeding events).

3. OBJECTIVES

Primary

- Reduction of time-to-response, defined by the achievement of laboratory blood marker response, confirmed at 48 hours after the initial reporting of this response

Secondary (including longer-term disease sequelae)

- Improvement in number of subjects responding to therapy
- Reduction in PE procedure-related items
- Reduction of time to resolution or improvement of symptoms typical of TTP, including blood markers
- Reduction of number of exacerbations (defined as recurrent thrombocytopenia following a response and requiring a re-initiation of daily PE treatment after ≥ 1 day but ≤ 30 days after the last daily PE) and relapses (defined as *de novo* event of TTP that occurs later than 30 days after the last daily PE)
- Improvement of cognitive level at steady state post acute phase
- Improvement of clinical symptoms and organ function
- Reduction in mortality within the PE treatment period and within the subsequent study drug treatment period (including tapering)
- Reduction of concomitant treatment-related complications
- Evaluation of safety and immunogenicity of adjunctive treatment with ALX-0081
- Determination of PK and PD characteristics of ALX-0081 in patients with acquired TTP

4. TRIAL DESIGN

4.1 Study Endpoints

4.1.1 Primary Endpoint

- Time-to-response, based on the following criteria:
 - Recovery of platelets $\geq 150,000/\mu\text{L}$
 - This response must be confirmed at 48 hours after the initial reporting of platelet recovery equal to or above $150,000/\mu\text{L}$ by a *de novo* measure of platelets $\geq 150,000/\mu\text{L}$ and LDH $\leq 2 \times \text{ULN}$ (i.e. “confirmed platelet response”)

4.1.2 Secondary Endpoints

All endpoints achieved within 30 day period after end of study drug treatment:

- Number of subjects with complete remission (defined as confirmed platelet response and absence of exacerbation)
- Number of (subjects with) exacerbations of TTP (defined as recurrent thrombocytopenia following a confirmed platelet response and requiring a re-initiation of daily PE treatment after ≥ 1 day but ≤ 30 days after the last daily PE) and time to first exacerbation of TTP
- Number of subjects relapsing of TTP (defined as *de novo* event of TTP that occurs later than 30 days after the last daily PE)
- Number of daily PE sessions, number of plasma units administered and number of days of daily PE
- Resolution of non-focal neurological symptoms as defined by neurocognitive function at complete remission, measured by a neurocognitive test battery
- Resolution or improvement (improvement of ≥ 1 grade in the CTCAE v4.0 scale) of TTP-related signs and symptoms as captured on physical examination and as adverse events, at complete remission and at end of the study drug treatment period (including tapering) (by number of unique subjects and by total number of AEs)
- Total mortality within the PE treatment period and within the subsequent study drug treatment period (including tapering)
- Incidence of PE treatment-related AEs, such as, but not restricted to: haemorrhage from catheter insertion, sepsis, catheter thrombosis, pneumothorax, fluid overload, hypoxia, hypotension, anaphylactoid reactions and TRALI

- Incidence and severity of ALX-0081 treatment-emergent AEs and relationship to study drug
- Development of ADA \leq 30 days post-last study drug treatment
- PK and PD profile

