8.3.3 Bleeding Events

Clinically relevant bleeding

Incidence of clinically relevant bleeding will be reported. Clinically relevant bleeding is defined as moderate to severe (including life-threatening) bleeding requiring urgent medical and/or surgical intervention.

Modified ITP bleeding score

Bleeding will also be measured using a modified version of the immune thrombocytopenic purpura (ITP) bleeding score. The rationale for using a modified version of the ITP bleeding score is the following. Both the WHO bleeding scale and other bleeding scales used in the frame of cardiac intervention or treatment of venous thromboembolism include bleeding or blood loss requiring transfusion of packed RBC or whole blood as a severity factor. It is common for subjects undergoing PE to need transfusions, even without apparent bleeding. The ITP bleeding score²⁷ does not include transfusion data. It is expected to be more sensitive than the other bleeding scales mentioned above. The modified ITP bleeding score is the sum of the scores for each line (Table 15).

Table 15: Modified ITP bleeding score.

Grade	0	1	2
Skin: petechiae	None	Scattered petechiae	Diffuse petechiae
Skin: ecchymosis	None	1-5 bruises	>5 bruises with size > 2cm
Oral	None	1 blood blister or >5 petechiae or gum bleeding <5 min	Multiple blood blisters or gum bleeding >5 min
Epistaxis	None	Blood when blowing nose or epistaxis <5 min (per episode)	Epistaxis >5 min (per episode)
Ocular	None	Subconjunctival haemorrhage	
Intracranial	None		Haemorrhage
Gastrointestinal	None	Blood when wiping	Blood present on stool
Urinary	None	Dipstick greater than trace	Macroscopic
Gynaecological	Normal period	Spotting outside of normal period	Bleeding greater than spotting outside of normal period, or very heavy period
Pulmonary	None	Haemoptysis	Haemorrhage

Clinically relevant findings that are observed prior to study drug initiation must be recorded on the relevant Medical History source documents page. Abnormalities in local tolerability will be reported via AE reporting throughout the trial. Clinically relevant findings found after study

drug initiation and meeting the definition of an AE (new AE or worsening of previously existing condition) must be recorded on an AE page of the source documents.

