9. SAFETY DEFINITIONS AND REPORTING REQUIREMENTS

9.1 Adverse Events

9.1.1 Definitions of Adverse Events

An AE is “any untoward medical occurrence in a patient or clinical investigation subject administered a study drug and which does not necessarily have a causal relationship with this treatment”. An AE can therefore be any unfavourable and unintended sign (including an abnormal laboratory finding), symptom, or disease temporally associated with the use of a study drug, whether or not related to the study drug.

A treatment-emergent AE is any AE temporarily associated with the use of a study drug, whether or not considered related to the study drug.

AEs include:

- Exacerbation of a pre-existing disease
- Increase in frequency or intensity of a pre-existing episodic disease or medical condition
- Disease or medical condition detected or diagnosed after study drug administration even though it may have been present prior to the start of the study
- Continuous persistent disease or symptoms present at baseline that worsen following the start of the study
- Lack of efficacy in the acute treatment of a life-threatening disease
- Events considered by the Investigator to be related to study-mandated procedures
- Abnormal assessments, e.g., ECG, vital signs or physical examination findings, must be reported as AEs if they represent a clinically significant finding that was not present at baseline or worsened during the course of the study
- Laboratory test abnormalities must be reported as AEs if they represent a clinically significant finding, symptomatic or not, which was not present at baseline or worsened during the course of the study

AEs do not include:

- Medical or surgical procedure, e.g., surgery, endoscopy, tooth extraction, transfusion. However, the event leading to the procedure is an AE. If this event is serious, the procedure must be described in the SAE narrative
- Pre-existing disease or medical condition that does not worsen
- Situations in which an adverse change did not occur, e.g., hospitalisations for cosmetic elective surgery or for social and/or convenience reasons, or elective

hospitalisation for observation in order to facilitate the follow-up when practical and logistical circumstances exist.

- Overdose of either study drug or concomitant medication without any signs or symptoms. However, overdose must be mentioned in the Study Drug Log

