#### **6.2.7 Medical Histories**

Medical history will be summarised for the safety population. The number and percentage of subjects for those who had any pre-study medical history and any pre-study medical history within each body system will be summarised by treatment group and overall. Those conditions that are reported as the underlying cause of TTP will be summarised separately. Subjects reporting more than one condition in a category will be counted only once for that category.

Medical history will be listed and will include reported body system, reported medical history term, date of onset, date of resolution, and ongoing status. An asterisk or an extra Y/N column indicating each line of medical history that is checked off as TTP related equal to Y will be placed.

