The number and percentage of unique subjects with resolved or improved TTP-related signs and symptoms as captured on physical examination and as adverse events within the PE treatment period, within the ensuing 30 days and at the one month follow-up will be summarised by treatment and overall along with the exact binomial CI of the percentage. Improvement of physical examination is defined as progressing from an abnormal to a normal result for a particular system at a given time point. Resolution of physical examination is defined as having normal results for all systems at a given time point. Resolution of an adverse event is defined as having a stop date present and an outcome of either 'resolved' or 'resolved with sequelae' within the given period. Both physical examination systems and adverse events flagged as being related to TTP will be considered.

The number and percentage of deaths within the PE treatment period, within the ensuing 30 days (study treatment period) and within the period from the end of the study treatment period up to and including the one month follow-up will be presented for each treatment group and overall for the ITT population only. Each death will be categorised into one of the distinct periods identified above, such that the death is counted only once in the table.

The incidence of PE treatment-related AEs, such as, but not restricted to: hemorrhage from catheter insertion, sepsis, catheter thrombosis, pneumothorax, fluid overload, hypoxia, hypotension, anaphylactoid reactions and transfusion related acute lung injury (TRALI) will be summarised by system organ class, preferred term, treatment group and overall. The summary will be repeated for PE treatment-related SAEs for the ITT population only.

---

Frequency tables (with accompanying Chi-square p-values) will be made for the following characteristics: use of corticosteroids during daily PE, use of rituximab during daily PE and tapering. Use of corticosteroids will be determined by using the Concomitant Medications data (both PE related and not PE related) with ATC codes beginning with “H02” (systemic corticosteroids). Use of rituximab will be determined by using the Concomitant Medications data (both PE related and not PE related) with ATC code “L01XC” (coded term “RITUXIMAB”).

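### The secondary objective on speed of TTP symptom resolution gets status counts only in the visible plan, and the adverse-event half of those counts omits most presenting signs

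*Protocol*

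**What the plan says.** **Objective.** Protocol section 3 lists as a secondary objective: "Reduction of time to resolution or improvement of symptoms typical of TTP, including blood markers". SAP 1.1 has the same objective and adds signs to symptoms.

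**Endpoint.** Protocol 4.1.2 takes "TTP-related signs and symptoms as captured on physical examination and as adverse events, at complete remission" and at the end of the study drug period, counted by subject and by event.

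**Analysis.** SAP 6.3.2 gives numbers and percentages of subjects with exact binomial intervals, for three windows: the plasma exchange (PE) period, the 30 days after it, and the one-month follow-up. On sources it says: "Both physical examination systems and adverse events flagged as being related to TTP will be considered". An examination system improves when it goes from abnormal to normal. Examination resolution means all systems are normal at the time point. An adverse event (AE) resolves when it has a stop date and a resolved outcome. SAP 6.1.5 drops CTCAE grade improvement for AEs because the grade is recorded once. Unless stated otherwise, the denominator is everyone in the population (SAP 6.1.1).

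**What counts as an AE.** Protocol 9.1.1 excludes: "Pre-existing disease or medical condition that does not worsen". It includes "Continuous persistent disease or symptoms present at baseline that worsen following the start of the study", and also "Disease or medical condition detected or diagnosed after study drug administration", even if already present before the study. For bleeding, Protocol 8.3.3 says: "Clinically relevant findings that are observed prior to study drug initiation must be recorded on the relevant Medical History source documents page".

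**The concern.** The objective is about speed, and the visible analysis is about status. A drug that clears signs sooner but leaves the same share cleared by a given visit would show no benefit.

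The AE half adds a second problem. Subjects are symptomatic on entry (Protocol 4.2), yet a presenting sign that simply clears never becomes an AE and so never becomes a resolved one. What this half mainly collects is TTP events that start, worsen or are first detected on study. Recovery from those events is then scored as success, although an effective drug should make the events rarer.

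At stake is the reading of one secondary endpoint. Taken at face value, its percentages could miss a real gain in speed or point against the better arm.

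**Working it through.** **1. Objective against analysis.** SAP 6.3.1 plans Kaplan-Meier and log-rank for platelet response. SAP 6.3.2 applies the same method to time to first exacerbation and plots time to first relapse. For signs and symptoms it plans neither a curve nor a median nor a test. Its three windows also differ from the protocol's two time points, and SAP 6.1.5, which lists changes from the protocol, does not mention this.

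**2. The plan's figure.** No figure is given for this endpoint. The medians used below come from the sample size for the primary endpoint (Protocol 10.4), which reproduces. With hazard ratio 6/3.36 = 1.786, 80% power and one-sided 2.5%, the Schoenfeld formula gives 4 × (1.960 + 0.842)² / (ln 1.786)² ≈ 94 events. Then 94/0.85 = 111, against the stated 110.

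**3. AE half with everyone in the denominator.** Percentage resolved = (share of subjects with a new TTP-related AE) × (share of those that resolve). The documents give neither input, so both are assumed.

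| New TTP-related AE | 70% resolve | 80% resolve | 90% resolve |
|---|---|---|---|
| 10% of subjects | 7% | 8% | 9% |
| 40% of subjects | 28% | 32% | 36% |

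At every assumed share, the arm with more deterioration scores higher.

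**4. PE-period window.** Stopping daily PE depends in part on the platelet count (Protocol 4.3), so a drug that speeds platelet recovery shortens this window. Assume window lengths equal to the design medians (6 and 3.36 days) and exponential symptom resolution. The share resolved is 1 − 2^(−window/symptom median).

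| Symptom median, placebo / ALX-0081 | Placebo, 6-day window | ALX-0081, 3.36-day window |
|---|---|---|
| 3 / 3 days | 75% | 54% |
| 6 / 6 days | 50% | 32% |
| 12 / 12 days | 29% | 18% |
| 6 / 3.36 days | 50% | 50% |

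In the first three rows the arms have identical symptom courses, and the count goes against the drug. In the last row a 44% shorter symptom median disappears.

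**5. Examination half.** Examinations are done at screening and baseline, daily during daily PE, the day after, then weekly (Protocol 8.1.2; SAP 6.4.2), with a category for findings related to TTP. This half therefore sees entry signs, and a time to normal can be derived from it. Its definition of resolution, as worded, names no baseline abnormality, so the choice of denominator matters here too.

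**The case against.** The strongest reply is that the endpoint has two sources and the examination half does what the AE half cannot. A subject who presents confused and then clears can score through the neurological or psychiatric system, and the Glasgow Coma Score is summarised by visit (SAP 6.3.3). This stands. It limits the criticism of the event set to the AE half.

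The AE exclusion is also not absolute. Presenting signs that worsen, or are first detected after dosing, do count. So this half omits most presenting signs, not all of them.

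Part of the objective does have a time analysis. Blood markers are named in it, and time to platelet recovery, confirmed with LDH, is the primary endpoint. LDH enters there only as a confirmation criterion. SAP 6.3.5 and 6.3.6 are redacted, so a time analysis of symptoms there cannot be ruled out.

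Finally, secondary p-values are labelled exploratory and the trial is powered only for the primary endpoint (SAP 6.3.2). That keeps the point modest. It does not supply the missing analysis.

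**Conclusion.** The concern holds within limits. In the text that can be read, the part of the objective beyond platelets is not answered by the planned analysis. The AE half mainly measures recovery from on-study deterioration, and the PE-period window depends on treatment. Both can push the percentages against the better arm. The sizes shown (8% against 32%; 50% against 32%) are illustrations on assumed incidence, resolution shares and exponential times. They are not forecasts.

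Two stronger readings are not supported.

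- A reader might infer that the trial cannot answer the objective. The baseline and daily examinations show that it can, with a different analysis.
- A reader might infer that late counts are bound to saturate and that a log-rank test would have about 79% power. At day 36 the design medians give 1 − 2^(−36/6) = 98.4% and 1 − 2^(−36/3.36) = 99.9%. But these are platelet-response medians, and nothing in the documents says symptoms follow them. Protocol 2.5.2 describes cognitive complaints lasting many years. The 79% is the primary endpoint's own power, from 110 × 0.85 × 0.983 = 91.9 events, and assumes that every subject has a qualifying sign.

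No power should be claimed, because the number of subjects with a qualifying sign is not given.

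**What to change.** Amend SAP 6.3.2 as follows.

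1. In subjects with at least one TTP-related examination system abnormal at baseline, analyse time from first study drug to the first visit at which all those systems are normal. Use Kaplan-Meier with the primary analysis's stratification (one PE session before randomisation or none), labelled exploratory, and state how deaths before resolution are handled.
2. For the examination status counts, use subjects abnormal at baseline as the denominator, and fixed windows from first dose in place of the PE period. Reconcile these windows with the protocol's two time points and record the change in SAP 6.1.5.
3. Report new or worsened TTP-related AEs separately as an incidence, with resolution among those events as description only.

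The baseline set should not rest on Medical History. SAP 6.2.7 provides for a mark "indicating each line of medical history that is checked off as TTP related equal to Y will be placed", but that section also deals with underlying causes of TTP, so the flag may mark causes rather than presenting signs. Medical history is also scheduled only at screening.

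The cost is SAP wording and a few extra outputs from data already collected. The downside is that resolution times become coarser, weekly instead of daily, once daily PE stops. That may happen earlier on ALX-0081, so the times should be read, or analysed, as interval-censored.
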